#### Background & Purpose of the Research

Describe the purpose, specific aims or objectives and specify the hypotheses or research questions to be studied:

Aim 1: Quantify the neurological and functional improvements due to BCI-FES dorsiflexion therapy compared to dose- and intensity-matched conventional therapy. Hypothesis: The neural repair mechanisms underlying BCI-FES dorsiflexion therapy will lead to improvements in neurological and functional outcomes that are greater and longer-lasting than those achieved by dose-matched conventional therapy. Aim 2: Identify stroke features that are linked to responsiveness to BCI-FES dorsiflexion therapy. Hypothesis: Based on preliminary studies, baseline gait velocity, dorsiflexion AROM/torque, TA muscle electromyogram (EMG) and motor evoked potentials, the magnitude of EEG alpha- and beta-band ERD/ERS during attempted dorsiflexion, and sensory function will influence the response to BCI-FES dorsiflexion therapy. Aim 3: Investigate the mechanism of action of BCI-FES dorsiflexion therapy. Hypothesis: BCI-FES therapy reinforces the connectivity between foot M1 and the  $\alpha$ -MN due to Hebbian plasticity. The study will have a significant impact in rehabilitative neuroscience, clinical neurorehabilitation,

Provide the scientific or scholarly rationale for the research and describe the relevant background information and the specific gaps in current knowledge that this study intends to address:

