Aim 1: The primary outcome measure will be gait velocity, which is directly linked to disability and social re-integration after stroke. Gait velocity will be assessed by measuring the time to traverse the middle 6 m of a 10-m walkway (5 repetitions/assessment). Secondary outcomes include: 1. Gait endurance: The distance walked over 6 minutes. 2. Fall Frequency: Number of falls experienced weekly. 3. Leg Motor Fugl-Meyer (FM) Score: Assessed according to the FM rating system. 4. Dorsiflexion Active Range of Motion (AROM) and torque: The paretic foot will be placed in an articulated brace which maintains the ankle at neutral during idling, while fixing the tibia perpendicular to the ground and the femur horizontal to the ground. The brace will be instrumented with an electro-goniometer and torque meter to automatically measure the maximum dorsiflexion AROM and torque (over 3 trials). 5. EEG Map: Subjects will undergo 64-channel EEG recording as they engage in 100 alternating 10-s long epochs of idling and attempted dorsiflexion. The EEG ERD/ERS, defined as the drop/rise in alpha (8-12 Hz) and beta (13-30 Hz) band power during attempted dorsiflexion (compared to idling), will be calculated and averaged over all epochs and across all channels. A pre-intervention baseline for each outcome will first be established. Subsequently, measurements will be performed at 1 week intervals during the intervention phase (total of 3), immediately after the intervention phase, as well as 1 and 3 months after completion of interventions. The primary efficacy outcome and endpoint will be gait velocity immediately after the intervention phase. Aim 2 (subgroup analysis of Phase II clinical trial) Since stroke is a heterogeneous disease, responsiveness to rehabilitation therapy is not uniform across all subpopulations. Hence, it is important to ensure that any new therapy, e.g. BCI-FES therapy, is matched to subpopulations that will benefit the most. The following set of baseline characteristics will be assessed during the pre-intervention phase (Fig. 6, Phase 2) for Groups 1 and 2 to determine which features influence responsiveness to BCI-FES therapy: 1. Baseline gait velocity, dorsiflexion AROM and torque: Baseline gait velocity and dorsiflexion AROM and torque will be taken from Aim 1. 2. TA volitional electromyogram (EMG): TA EMG will be assessed by having subjects attempt dorsiflexion while seated with tibia perpendicular to ground. EMG will be acquired by a bioamplifier with surface electrodes placed over the TA muscle. Subjects will be categorized as either

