#### **Statistical Considerations**

Is a statistical analysis plan appropriate for this qualitative study design?

Yes

Describe the statistical methods for the stated specific aims and hypotheses. Your analysis plans should match the stated study specific aims and hypotheses:

Aim 1: The study design is a parallel randomized controlled trial with two arms: BCI-FES dorsiflexion therapy and dose-matched conventional physical therapy. A total of 80 subjects (which includes 10% attrition) will be randomized with 1:1 ratio into the two study arms. The primary outcome is gait velocity and the secondary outcomes are gait endurance, fall frequency, leg motor FM score, and dorsiflexion AROM and torque. Outcomes measures will be evaluated at baseline, weekly during therapy, immediately post-intervention, and 1- month and 3-months post-therapy. The primary efficacy analysis (with intent-to-treat analysis with respect to treatment randomized) will be based on a linear mixed model (LMM) with gait velocity measured at baseline weeks 1-4 (time 0, 1, 2, 3, and 4) with time, treatment group and group by time interaction assess the difference in the rates of change (improvement) in gait velocity between treatment groups. Model estimation will be based on restricted maximum likelihood (REML) with unstructured covariance among repeated measurements over time. The LMM will also be applied to evaluate group difference for secondary outcomes and secondary endpoints at 1- and 3-months post-therapy. In order to determine if  $\mu$  and  $\beta$  ERD/ERS significantly changes over the 4 weeks of therapy, the ERD and ERS magnitude will be calculated for each EEG channel across all attempted dorsiflexion epochs, and for each assessment. The Mann-Whitney U test will be used to determine if any significant changes in the magnitude of ERD/ERS at each assessment with respect to the baseline. Based on the findings, each subject will be categorized as demonstrating significant changes in ERD/ERS or not. Next, all subjects will also be categorized on whether they experienced a detectable increase in gait velocity (defined as an increase in gait velocity of  $>0.16$  m/s with respect to baseline). A Chi-square test will be used to assess if there is a difference between the proportion of those with changes in ERD/ERS magnitude in those who had gait improvement within the BCI- FES therapy group. This will also be repeated for the control group. In addition, to determine if the presence of significant ERD/ERS changes was affected by group, the Chi-square test will be repeated by using BCI-FES group as the observation and the control group as the expected values. Aim 2: Data from Aim 1 will be used for analysis in this aim. The primary outcome is gait velocity immediately post-BCI-FES therapy, and the secondary outcomes are the same as in Aim 1. To test whether specific stroke features (e.g. baseline gait velocity, dorsiflexion AROM, etc.) modify response to treatment over

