**Power Analysis:** For Aims 1 and 2, the power analysis was based on a LMM with two treatment groups and 5 repeated measures (baseline and after weeks 1-4) with a significance level of 0.05. Previous studies have examined the clinically meaningful gait improvement (minimal clinically important difference) of 0.16 m/s, including a multicenter randomized clinical trial that includes conventional physical therapy. Thus, to ensure clinically meaningful effect size, we assume conventional therapy will have an improvement of 0.25 m/s after 4 weeks of treatment. Data from prior studies as well as our own preliminary data (n=9) found that the between-subject variance in gait velocity of about 0.16 m/s and the within-subject correlation of about 0.95. Table 1 below shows the power to detect improvement of BCI-FES over conventional therapy of 30% - 40%. Thus, for the proposed study with n=80 patients (40 per arm) has 92% to 94% power to detect an effect size/improvement of 35% for various between-subject variance (0.15 m/s to 0.17 m/s) in determining treatment efficacy (Aim 1). We note that n=80 total has been intentionally inflated in order to accommodate the objectives of aim 2 to examine modifying factors, such as TA MEP (primary modifying factor), on treatment. That is, for n=30 per arm the power to determine efficacy (aim 1) is 85% for detecting an effect size/improvement of 35% (between-subject variance 0.16 m/s); thus, increasing to n=40 allows for detecting modifying factor on treatment (aim 2) when the interaction effect smaller (effect size 28% can be detected with 79% power). Table 1: Power to detect improvement in gait velocity due to BCI-FES over conventional therapy for n=80 with various between-subject variance (aim 1). Between-Subject Variance Effect Size (Improvement) 0.15 0.16 0.17 30% 87.3% 85.2 % 83.0% 35% 94.5% 93.5% 92.1% 40% 98.3% 97.7% 97.0% Aim 3: Total sample size of n=20 will have 82% power to detect an R-square of 0.16 (attributed to the effect of interest, e.g., w x group) adjusted for baseline measurement and main effects whose total contribution R-square is 0.5 (for 3 independent variables) in a multiple regression model.

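### Aim 1 hypothesises gains that last longer than control gains, but the planned follow-up analysis can show only that a benefit is still present at 1 and 3 months

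*Combined protocol and SAP*

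**What the plan says.** - **Hypothesis** (Background & Purpose of the Research, Aim 1): improvements under BCI-FES will be "greater and longer-lasting than those achieved by dose-matched conventional therapy". This makes two claims, one about size and one about duration.
- **Visits** (Study Design, endpoint definitions): after baseline and weekly measurements, outcomes are taken "immediately after the intervention phase, as well as 1 and 3 months after completion of interventions".
- **Primary endpoint** (same section): "The primary efficacy outcome and endpoint will be gait velocity immediately after the intervention phase".
- **Primary model** (Statistical Considerations, Aim 1): a linear mixed model (LMM) over baseline and weeks 1 to 4, "with time, treatment group and group by time interaction assess the difference in the rates of change (improvement) in gait velocity between treatment groups".
- **Follow-up analysis** (same section): "The LMM will also be applied to evaluate group difference for secondary outcomes and secondary endpoints at 1- and 3-months post-therapy".

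The documents do not define longer-lasting, a retention measure, a contrast from end of therapy to follow-up, or a decision rule for durability. The power analysis covers only baseline to week 4.

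**The concern.** The claim of greater gains has a matching test, the group-by-time comparison up to week 4. The claim of longer-lasting gains has none. The group difference at 3 months carries forward whatever difference existed when therapy stopped. It can be positive when both arms change identically after therapy, and also when BCI-FES gains fade faster but remain ahead. A significant 3-month difference could therefore be read as support for the duration claim when the data speak only to size. The form asks that analysis plans match the stated aims and hypotheses, and on this half of the hypothesis they do not.

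**Working it through.** **Inputs**
- Control gain: "we assume conventional therapy will have an improvement of 0.25 m/s after 4 weeks of treatment" (Power Analysis).
- Effect: 35% of 0.25 = 0.0875 m/s at week 4.
- Between-subject variance 0.16 (SD 0.40 m/s) and within-subject correlation 0.95 (Power Analysis). The correlation is given for the five measures from baseline to week 4. No value is given for 1 or 3 months, so 0.95 is carried forward as an assumption and varied below.
- Test level: "with a significance level of 0.05". Sidedness is not stated. Two-sided is assumed because it reproduces the plan's table.
- Size: 40 per arm planned. The Progress Report gives 62 randomised in Aim 1, taken here as 31 per arm. The split is not stated, and withdrawals would lower the number at follow-up.

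**Reproducing the plan's figure.** For a slope difference over t = 0 to 4 (sum of squared deviations 10), with residual variance 0.16 × 0.05 = 0.008:
- SE = sqrt(2 × 0.008 / (40 × 10)) = 0.00632.
- Slope difference = 0.0875 / 4 = 0.0219, so z = 3.46.
- Power = Φ(3.46 − 1.96) = 93.3%, against 93.5% stated. The other eight cells of Table 1 also agree within 2 points.

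**What the follow-up test measures.** Let D4 be the between-arm difference in gain at end of therapy, and R the between-arm difference in change from end of therapy to follow-up. The group difference in gain at follow-up is D4 + R. Durability concerns R alone.

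**Rejection rate of the planned test.** With two visits, the SD of a change is sqrt(2 × 0.16 × 0.05) = 0.1265 m/s. The SE of the arm difference is sqrt(2 × 0.016 / n), which is 0.0283 at n = 40 and 0.0321 at n = 31. Power = Φ(d/SE − 1.96).

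| Scenario at one follow-up visit | d (m/s) | 40 per arm | 31 per arm |
|---|---|---|---|
| Week-4 difference carried forward (R = 0), correlation 0.95 | 0.0875 | 87% | 78% |
| Same, correlation 0.90 (SD of change 0.179) | 0.0875 | 59% | 49% |
| Same, correlation 0.85 (SD of change 0.219) | 0.0875 | 43% | 35% |
| Both arms keep 80% of their gain, correlation 0.95 | 0.0700 | 70% | 59% |

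In the last row BCI-FES loses 0.0675 m/s and control loses 0.0500 m/s, so R = −0.0175. The test is still positive in most trials. With equal proportional loss, the rate drops below half once less than about 63% of the gain is kept (1.96 × 0.0283 / 0.0875) at 40 per arm, or 72% at 31 per arm.

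If the 3-month comparison ignored baseline (SD 0.40), the first scenario would reject in only 16% of trials at 40 per arm. That test would not measure retention either.

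**The retention contrast R.** By simulation at 40 per arm, when the week-4 difference is carried forward it rejects in 5% of trials. Its 80%-power difference is (1.96 + 0.84) × SE:
- 0.079 m/s at 40 per arm and 0.090 m/s at 31 per arm.
- If the correlation between end of therapy and follow-up were 0.90, both grow by sqrt(2), to about 0.112 and 0.127 m/s.

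**The case against.** **Longer-lasting may mean only still different at 3 months.** If both arms lose the same number of m/s per month, the larger gain also stays above baseline longer, which is longer-lasting in an ordinary sense. The lay summary speaks of lasting gains, and the background contrasts lasting improvement with orthoses whose benefit goes when they are removed. A difference still present at follow-up answers both. This stands as a reason to offer rewording as a remedy. It does not remove the mismatch, because the Aim 1 hypothesis compares duration with control and no passage narrows it.

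**The contrast has its own bias.** It measures absolute loss. If both arms keep 50% of their gain, BCI-FES falls by 0.169 m/s (half of 0.3375) and control by 0.125. The contrast is then about −0.044 m/s and significant in about 34% of trials at 40 per arm, almost all against BCI-FES. This stands, so proportions kept must be shown alongside.

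**The contrast is underpowered.** If control loses 0.05 m/s and BCI-FES loses nothing, power is 42% at 40 per arm and 34% at 31 per arm. This also stands.

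**A stronger reading that fails.** A reader might infer that the plan could miss true durability when the arms are equal at the end of therapy and separate later. It would not. In that case D4 = 0, so the group difference in change from baseline and the retention contrast have the same expected value and, under the plan's variance model, the same SE. Their power is equal.

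**Conclusion.** The mismatch holds. The planned follow-up analysis cannot separate a gain that lasts longer from an end-of-therapy difference carried forward. This follows from the structure of the comparison and needs no numerical assumption.

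The percentages do need assumptions: that the 35% effect is real, that the comparison is change from baseline, and that the correlation extends to follow-up. With the week-4 difference carried forward they run from 87% (correlation 0.95, 40 per arm) down to 35% (correlation 0.85, 31 per arm). A reader might take 87% as a false-positive rate for a durability claim. The documents do not support that. No passage commits the investigators to concluding longer-lasting from these tests, and with no treatment effect at all the rejection rate is about 5% per visit.

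The 1- and 3-month comparisons are secondary. The primary end-of-therapy analysis, the sample size and the data collection are unaffected. A change is still worth making, because half of the stated Aim 1 hypothesis has no matching test and the remedy is cheap.

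**What to change.** Before analysis, in Statistical Considerations, Aim 1:

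1. Report the 1- and 3-month group differences as a difference still present at that visit.
2. Base any longer-lasting statement on a prespecified contrast from an LMM with visits as categories through 3 months: (3 months minus immediately post-therapy) in BCI-FES versus control, and likewise at 1 month, each with its confidence interval.
3. State that this contrast measures absolute retention. Show the proportion of gain kept in each arm beside it, because equal proportional loss pushes the contrast against the arm with the larger gain.

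Alternatively, reword the hypothesis so that it claims gains that are greater and still present at 1 and 3 months. The planned analysis then fits.

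**Cost.** No new data or visits are needed, and at the renewal the Progress Report still listed data analysis as work to come. The price is a narrower claim. The contrast reaches 80% power only at about 0.079 m/s (40 per arm) or 0.090 m/s (31 per arm), close to the whole planned treatment effect of 0.0875 m/s. Longer-lasting may remain unproven, and the report should say that a null result is not evidence of equal durability.

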#### **Subject Population(s) (Individuals/Records/Biospecimens)**

Check all subject populations/data sources that apply to the research:

Adults Competent to Provide Informed Consent

---

#### **Maximum and Expected Number of Persons/Records/Biospecimens to be Enrolled**

1. Click "Add Line" button above Enrollment Table to add a Category/Group
  - a. To change visibility of columns, click "Columns" button above Enrollment Table and select which Column rows to view.
2. Specify the maximum and expected numbers of individual-level information and/or biospecimens to be accessed/analyzed within each Category/Group

---

Category/Group

Adults (Aim 1 and 2)

Age Range

18-80

Maximum Number of Subjects, Subjects to be Consented or Reviewed/Collected

200

Number Expected to Complete the Study or Needed to Address the Research Question

80

Category/Group

Adults (Aim 3)

Age Range

18-80

Maximum Number of Subjects, Subjects to be Consented or Reviewed/Collected

40

Number Expected to Complete the Study or Needed to Address the Research Question

20

Will this study only take place at UCI and does not involve other sites?

Yes

#### Eligibility Factors (Inclusion/Exclusion Criteria)

1. Click "Add Line" button above Eligibility Factors Table to add a inclusion/exclusion criteria
  - a. To change visibility of columns, click "Columns" button above Eligibility Factors Chart and select which Column rows to view.
2. Identify the factors for limited eligibility and provide a scientific rationale. Include additional rows for factors, as needed.

---

Category/Group Eligibility

Adults - all groups

Inclusion Criteria

1. Age 18-80 years inclusively at time of consent;
2. Radiologically confirmed stroke, ischemic or intracerebral hemorrhage (ICH) in etiology, with day of onset at least 26 weeks prior to day of randomization
3. Gait velocity < 0.8 m/s at screening and baseline visits.
4. Foot-drop in affected limb as defined by dorsiflexion active range of motion (AROM) via goniometry in seated position foot dangling is less than passive range of motion and less than 15 degrees.
5. Plantarflexors spasticity < 3 on modified Ashworth Scale;
6. Can walk > 10 m (with or without ankle foot orthosis (AFO), and cane or walker permitted) at a supervised level;
7. Can tolerate FES with pain no more than 4 on pain analog scale and has adequate muscle response of dorsiflexion  $\geq$  10 degrees;
8. Passive Range of Motion at least 0 degrees ankle dorsiflexion in subtalar neutral or with FES

#### Exclusion Criteria

Exclusion Criteria: 1. A major, active, coexistent medical, neurological (apart from stroke) or psychiatric disease (apart from stroke), including alcoholism or dementia, orthopedic injuries, that substantially affects gait. \*\*Because old orthopedic injuries may or may not affect gait, at the discretion of the site's study PI, exclusion criterion #2 related to orthopedic injuries can be waived if the joint/muscles are back to normal motor and range of motion function. 2. A major medical disorder that substantially reduces the likelihood that a subject will be able to comply with all study procedures or safely complete study procedures. This includes, but not limited to documented serious cardiac conditions, serious pulmonary conditions, legal blindness, end stage renal or liver disease, pulmonary embolism or deep venous thrombosis. 3. Resting systolic blood pressure above 170, diastolic blood pressure above 100 at screening and baseline evaluations 4. Implanted electronic device (e.g. pacemaker) or skull metallic implants (e.g. cranioplasty plate covering the leg motor area) with which study research procedures are contraindicated or incompatible. 5. Deficits in communication that interfere with reasonable study participation: language or attention impairment (score>1 on NIH Stroke Scale items 9 and 11, respectively) 6. Significant cognitive impairment, defined as Montreal Cognitive Assessment score < 22 (For those with aphasia: \*\*Because Montreal Cognitive Assessment scores may be difficult to interpret for patients with aphasia, at the discretion of the site's study PI, exclusion criterion #5 ("MoCA score cannot be <22") can be waived) 7. A new symptomatic stroke occurs apart from the index stroke during the screening process and prior to randomization 8. Life expectancy < 6 months 9. Skin breakdown over electrical stimulation sites; 10. Received chemical denervation (eg Botox) to legs in the preceding 6 months, or expectation that chemical denervation will be administered to the leg prior to expected completion of the study 11. Unable or unwilling to perform study procedures/therapy, or expectation of non-compliance with study procedures/therapy 12. Pregnancy; 13. Significant pain (visual analog scale >4), chest pain, or shortness of breath with walking. 14. Receiving any outside concurrent physical therapy involving the lower extremities after enrollment in the study up to 1 month post treatment 15. Any general medical condition and psychosocial situation that substantially interferes with reasonable participate in study appointments 16. Non-English

speaking, such that subject does not speak sufficient English to comply with study procedures 17. Concurrent enrollment in another investigational interventional study 18. Severe depression, defined as Geriatric Depression Scale Score >11: \*\*Because Geriatric Depression scale scores may be difficult to interpret for some patients, at the discretion of the site's study PI, exclusion criterion #17 ("Geriatric Depression score cannot be >11") can be waived) 19. Concurrent use of FES orthosis for gait. 20. A new symptomatic stroke occurs apart from the index stroke during the screening process and prior to randomization If TMS Eligible (note that potential subjects who do not qualify for TMS will not be excluded from the main study, they will only be excluded from undergoing TMS procedures): 21. TMS: Metallic hardware on the scalp (e.g. vascular clips or cranioplasty mesh) 22. TMS: Implanted medication pumps, intracardiac line, or central venous catheter 23. TMS: History of cortical stroke or other cortical lesion such as brain tumor 24. TMS: Prior diagnosis of seizure or epilepsy 25. TMS: Any electrical, mechanical, or magnetic implants 26. TMS: History of neurosurgery 27. TMS: uncontrolled Migraine headaches 28. TMS: Any current medications that affect seizure threshold such as tricyclic antidepressants and neuroleptics 29. TMS: Unstable medical conditions

Is eligibility based on age, gender, pregnancy/childbearing potential, social/ethnic group, or language spoken (e.g., English Speakers only)?

Yes

